### **For participants randomized to the Usual Care Arm:**

Participants randomized to the Usual Care arm of the study will receive eczema educational materials that are typically provided by their health care provider after a clinic (or telehealth) visit. Examples include an eczema action plan that is created by the provider with the patient and includes daily skincare as well as special skincare instructions for eczema flares, handouts on recommendations for dry skin, etc. Participants in the Usual Care arm will complete the same schedule of study surveys (see Table of Assessments below) as participants randomized to the CBT arm.

### **For participant randomized to the CBT Arm:**

Participants randomized to the CBT arm of the study will be contacted by their study therapist to complete an initial telehealth assessment (see Assessment Interview document) about understanding of AD, adherence to medication, strategies they use to

## Brief Cognitive Behavioral Therapy to Treat Itch Rumination “Itch CBT” in Eczema

cope with itch, social concerns, mood and anxiety concerns related to AD, sleep concerns, and areas of functional impairment due to AD.

Following their assessment, families will be instructed on how to download a free version of the Zoom application onto their internet-capable personal device, with specific details on how to connect for follow-up telehealth visits. Resources will be provided to families for technical support. Therapists will then follow up with participants for three sessions on a weekly basis via telehealth on Northwestern Zoom, which is encrypted to increase security and privacy. Sessions will include instruction on mindfulness-based activities, behavioral interventions to improve adherence, action planning during flares, and coping mechanisms to help cope with social challenges (see CBT Supplemental Materials). Participants will review the session with their parents, in conjunction with their therapist, and be given homework to complete for the following week. Following each therapy session, participants will complete study surveys via REDcap and at 4 weeks following the intervention. Participants will have up to 2 weeks to complete the follow-up questionnaires.

### Table of Assessments for Children:

Assessments:	Visit 1	Visit 2	Visit 3	Visit 4	Follow-Up
Itch Rumination Questionnaire - Child	X			X	X
Stigma Short-Form	X			X	X
PROMIS Pediatric Profile – Anxiety & Depression	X			X	X
PROMIS Sleep – Child	X			X	X
PROMIS Pediatric Itch	X			X	X
VAS Dose	X	X	X	X	X
POEM	X			X	X
Child’s Derm Life Quality Index (CDLQI)	X			X	X
Mood NRS	X	X	X	X	X
Itch Severity VAS	X	X	X	X	X
PROMIS Positive Affect	X			X	X
PROMIS Meaning and Purpose SF	X			X	X

### Table of Assessments for Parents/Guardians:

Assessments:	Visit 1	Visit 2	Visit 3	Visit 4	Follow-Up
Itch Rumination Questionnaire - Parent	X			X	X

## Brief Cognitive Behavioral Therapy to Treat Itch Rumination “Itch CBT” in Eczema

Parent Proxy Pediatric Itch – Short Form 1 (2+6)	X	X	X	X	X
PROMIS Parent Proxy – Anxiety & Depression	X			X	X
PROMIS Parent Proxy—Positive Affect	X			X	X
PROMIS Sleep - Parent	X			X	X
VAS Dose	X	X	X	X	X
Itch Severity VAS	X	X	X	X	X
Five Facet Mindfulness Questionnaire SF	X			X	X
PROMIS Family Relationships	X			X	X

### 5.4 Statistical Analysis Plan – Aim 2

Because this a clinical trial, our primary statistical approach will be a response profile analysis. In this model, the effect of treatment and other variables are used predict the outcome over time, but an influence of treatment is not posited for pre-treatment assessments. This method is recommended for analyzing clinical trials. We will include participants using the intent-to-treat criterion, in which all randomized participants are included in the analysis. All aspects of this clinical trial will be reported in accord with CONSORT guidelines. Although the response profile analysis will be our primary approach, we will also explore alternative approaches. Latent growth curve models use all available data (i.e., they do not discard observations with missing data) and provide valid inferences in the presence of missing outcome data under the missing at random (MAR) assumption.

The primary outcome measures will be the NRS Itch Severity and the CDLQI. All other questionnaires will be used as secondary outcome measures.

Primary outcomes:

1. NRS Itch Severity

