## Brief Cognitive Behavioral Therapy to Treat Itch Rumination “Itch CBT” in Eczema

behavioral, and relaxation strategies to combat itch rumination. With expert input from the National Eczema Association and our research team, we have formalized a protocol for Itch CBT. In our second aim, we will pilot the protocol in a brief (4 session) intervention as part of an interdisciplinary AD clinic, comparing Itch CBT to usual care (our standard educational handouts).

Because each group will have similar levels of eczema severity and will be receiving the same level of medical care, we will be able to attribute changes over time between the two groups to this mental health intervention. We predict that patients treated with Itch CBT will show significantly less itch and less severe itch, as well as significantly greater quality of life, at follow-up compared to those receiving standard treatment. Predicted secondary outcomes include decreased rumination on itch, sleep disturbance, depression, and anxiety, as well as improved medication adherence, and social/family functioning. This pilot study will allow us to measure itch rumination, its effects on children with AD, and the efficacy of Itch CBT in itch rumination. With this preliminary data, we can apply for NIH funding to provide more extensive evidence for the efficacy of Itch CBT in treating itch rumination; ideally we hope to develop an Itch CBT protocol that can easily be implemented by trained personnel in the clinic setting or even as an online tool for patients. The National Eczema Association is the perfect partner for our research team to help develop and disseminate this intervention.

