### 3.0 Hypothesis and Specific Aims

**Hypothesis:** Our overall hypothesis is that a brief CBT intervention to treat itch rumination is an effective adjunctive strategy to improve itch in AD.

**Aim 1:** Develop and refine a brief, user-friendly, easily deployable CBT intervention to treat itch rumination (Itch CBT) for pediatric AD. We will conduct semi-structured interviews of 20 patient/parent dyads to tailor a CBT rumination intervention for itch in AD to determine the best cognitive and behavioral strategies to implement in Itch CBT. Both open- and close-ended questioning will be used to allow for patient suggestions for new material, as well as input on proposed materials and strategies.

**Aim 2:** Determine the efficacy of the itch rumination intervention in reducing distress related to AD and itch, as well as correlates of AD that affect quality of life, such as social concerns and sleep disturbance. Preliminary data will also be collected to determine the validity of a child and parent-proxy questionnaire designed to measure rumination on itch in AD.

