## Brief Cognitive Behavioral Therapy to Treat Itch Rumination “Itch CBT” in Eczema

Patients are referred into this clinic through several “recruitment sites.” The diverse racial and ethnic demographics are summarized in Table I. The age group is chosen because all measures are validated in this age group, and cognitive interventions are easiest to implement in this narrow age group for a pilot study. Future work would expand to younger age groups.

**Table I.** Racial and Ethnic Demographics of Recruitment Sites

Recruitment Sites	African-American	Hispanic	Caucasian	Asian	Other
Clark-Deming Outpatient	36%	46%	15%	3%	<1%
Uptown Clinic	38%	35%	13%	9%	5%
La Rabida Hospital	74%	11%	8%	unknown	6%
Northbrook Lurie Outpatient	2%	7%	80%	6%	5%
Lurie Children's Outpatient	9%	23%	47%	4%	17%

A strength of this application is the volume and diversity of patients seeking treatment at the interdisciplinary pediatric allergy/dermatology clinic Lurie Children’s Hospital, allowing for a wide range of racial, ethnic, and socioeconomic diversity.

Participants in the active and control conditions will be matched for age, gender, and disease severity. All participants will be compensated \$25 for each visit for their time and to cover the cost of transportation. Inclusion and exclusion criteria are listed above in the previous section.

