## Brief Cognitive Behavioral Therapy to Treat Itch Rumination “Itch CBT” in Eczema

We plan to recruit 24 patient-parent dyads (48 total participants) stratified by child’s age ( $n = 6$ : 8-12,  $n = 6$ : 12-17 years) to the CBT itch rumination intervention. Usual care will be provided to 12 AD patients, matched on gender and itch severity. Itch severity will be based on the NRS Itch Severity score. Potential participants will be recruited from Lurie Children’s Dermatology and Allergy Departments. If patients have an upcoming clinic (or remote clinic visit) scheduled, they will be contacted prior to their clinic visit by a study coordinator/provider and will be provided with a brief description of the study to determine interest in order to allow patients to schedule sufficient time for study activities following their clinic appointment. If patients do not have an upcoming clinic visit, they will be contacted by phone by a study coordinator/provider and given a brief description of the study. If interested, participants will be screened using the inclusion/exclusion criteria (see Screening Questionnaire). If eligible, patients will be e-consented to the study using REDCap e-consent procedures by a study coordinator. A study coordinator will email a link to the e-consent form to the participant and then thoroughly explain the study, allowing time for participants to ask questions. If participant is still interested, they will be instructed to sign the e-consent form using the link. After participants have been e-consented, they will be randomized to one of the study conditions (usual care vs. CBT). Following e-consent, participants will be emailed a copy of their signed e-consent form. Following their clinic appointment, all participants will complete study questionnaires (see Table of Assessments below).

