**Randomization Procedures:** Participants will be randomized to one of two groups: (1) Itch CBT or (2) Usual care. Randomization will occur on a 1:1 ratio and within strata, which are gender (male vs. female) and Itch Numerical Rating Scale (4-6 vs. 7-10). Participants will be randomized to treatment based on a predetermined list within each strata created using the *blockrand* package of R. Randomization will occur by blocks, with varying block sizes, in accord with recommended methods for RCTs. The randomization key will be linked to a unique study ID number, as well as to a treatment condition (Itch CBT vs. Usual Care). Participants will be aware that there are different arms they can be assigned to and will know which randomization group they are assigned.

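### Section 5.4 names a model and two primary outcomes for an efficacy aim, but no success rule, alpha, tested contrast or identifiable itch measure

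*Combined protocol and SAP*

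**What the plan says.** Aim 2 in section 3.0 is to "Determine the efficacy of the itch rumination intervention in reducing distress related to AD and itch". Section 5.4 makes response profile analysis the primary approach, with no treatment effect posited before treatment and all randomised participants included. In that model, "the effect of treatment and other variables are used predict the outcome over time". It then states that "The primary outcome measures will be the NRS Itch Severity and the CDLQI", lists the two as items 1 and 2, and makes every other questionnaire secondary. It gives no alpha, hierarchy, decision rule, contrast or visit.

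The nearest thing to a criterion is in section 2.0, which predicts that treated patients "will show significantly less itch and less severe itch, as well as significantly greater quality of life, at follow-up".

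Sections 5.3 (recruitment and Randomization Procedures) and 5.4 refer to an itch NRS. The Table of Assessments for Children lists "Itch Severity VAS", and the parent table has the same entry. Neither table lists an itch NRS.

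On allocation, section 5.1 says "Participants in the active and control conditions will be matched for age, gender, and disease severity". Section 5.3 plans "24 patient-parent dyads (48 total participants) stratified by child’s age", with usual care matched on gender and itch severity. Randomization Procedures uses two factors only: gender, and itch NRS in bands 4-6 and 7-10.

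**The concern.** With two primary outcomes, what counts as a positive trial depends on the rule that joins them. If either outcome is enough, the chance of a false claim is about twice nominal. If both are needed, there is no inflation but power falls. Section 5.4 fits either rule, so a mixed result has no agreed reading.

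The response profile model leaves a second choice open: an overall group-by-time test, or the arm difference at one visit. The follow-up mentioned in section 2.0 could mean Visit 4 or the Follow-Up column. For the first primary outcome, a third choice is open: which instrument, and whether the child's or the parent's report counts. All of these could be settled after the data are seen, which would weaken the preliminary evidence that the trial is meant to supply for a grant.

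**Working it through.** **Inputs from the documents.** Section 5.3 gives 6 + 6 = 12 children on CBT and 12 on usual care; 12 + 12 = 24, consistent with 1:1 randomisation. After baseline, CDLQI is measured at Visit 4 and Follow-Up, and itch severity at Visits 2, 3, 4 and Follow-Up.

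**Assumptions, because the plan gives none.** Two-sided 0.05 per outcome; correlation between the two outcomes 0 to 0.7; correlation between baseline and later values (rho) 0.5 or 0.7; no dropout. Aim 2 has no stated error rate or power figure to reproduce.

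**1. Either outcome suffices, one unadjusted test each.**
- Independent tests: 1 − 0.95² = 0.0975.
- Correlated tests: 1 − P(|Z1| < 1.96 and |Z2| < 1.96), bivariate normal. This is 0.0951 at correlation 0.3, 0.0907 at 0.5 and 0.0835 at 0.7.
- Ceiling: 0.05 + 0.05 = 0.10.
- Simulation (12 v 12, baseline-adjusted Follow-Up contrast, 40,000 runs per setting): 8.4-10.0%. The exact overall test gives 9.1-10.0%.

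**2. Both required at 0.05.** P(both reject) = 1 − 2 × 0.95 + P(neither rejects).
- Correlation 0: 1 − 1.90 + 0.9025 = 0.0025.
- Correlation 0.7: 1 − 1.90 + 0.9165 = 0.0165.
- If only one null is true, the error is at most 0.05.

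**3. Holm.** The smaller p is tested at 0.025, then the other at 0.05. Under the joint null the error is 1 − 0.975² = 0.0494 at correlation 0 and 0.0430 at 0.7. Simulation gives 4.3-5.2%, which is 5% within simulation error.

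**4. Power of one baseline-adjusted visit contrast.** The standard error in SD units is about √[(1 − rho²) × 2/12].
- rho 0.5: √(0.75/6) = 0.354, so a 1 SD effect is 2.83 standard errors.
- rho 0.7: √(0.51/6) = 0.292, so 1 SD is 3.43 standard errors.
- A noncentral t on 21 df gives 77% and 90%. Simulation, which also allows for chance baseline imbalance, gives 75% and 89%.
- At 0.025 the simulated values are 64% and 82%. Holm's first step therefore costs 75 − 64 = 11 or 89 − 82 = 7 points if only one outcome responds.
- At 0.8 SD and rho 0.5, power falls from 56% to 44%, a loss of 12 points.

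Power when both outcomes must succeed at Follow-Up (range over outcome correlation 0 to 0.7):

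| Effect on each outcome | rho 0.5 | rho 0.7 |
|---|---|---|
| 1 SD | 56-65% | 79-83% |
| 0.8 SD | 31-43% | 53-61% |

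The low ends agree with independence: 0.75² = 0.56, 0.89² = 0.79, 0.56² = 0.31.

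**5. Stratification.** Section 4.1 admits a child on a POEM score or on an itch NRS of at least 4. The itch strata start at 4, so a child admitted on POEM with a lower itch score has no stratum. Age is a matching factor in section 5.1 and splits the CBT group in section 5.3, but it is not a randomisation stratum. Section 5.4 does not say which factors enter the model.

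A simulation of CDLQI power at 1 SD and rho 0.5 used four strata of six children split 3:3, which varying block sizes do not guarantee. Adjusting for gender and itch stratum raised power from 75.4% to 78.3%, or from 76.5% to 83.0%, when gender explained 10% or 20% of residual variance. When gender explained nothing, power went from 74.9% to 74.3%.

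**The case against.** The strongest reply is that this is a 24-child pilot meant to give preliminary data for a grant application, with no alpha or power claim for Aim 2, so confirmatory error control asks too much. Much of that stands. It is why an estimation-only declaration belongs among the remedies. It does not remove the gap, because section 3.0 speaks of determining efficacy and section 2.0 predicts significant differences.

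It is also fair to say that section 2.0 leans towards both outcomes at follow-up. It is a Background prediction and sets no rule. The age conflict is softer than it first looks: section 5.3 agrees with Randomization Procedures on gender and itch severity, and its 6 + 6 age split can be read as a recruitment quota. Section 5.1 still conflicts.

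A reader might infer several stronger things that the documents do not support:
- That no analysis method is given. Response profile analysis is named; what is missing is the contrast, visit and alpha.
- That the trial's error rate is already doubled. That follows only if either outcome suffices, which the plan does not say.
- That the error reaches 17-26%. That needs any of six visit contrasts (four itch, two CDLQI) to be picked after the data are seen, and the plan does not propose this.
- That the primary test is anti-conservative. An uncorrected chi-square test would be at this sample size, but the plan names no such test.
- That leaving out the strata inflates error. It does not; it can only cost power.

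**Conclusion.** The concern holds in this form: section 5.4 supplies a model and two primary outcomes but no success rule, alpha or named contrast, and its first primary outcome cannot be matched to one instrument and one reporter. With 12 per arm, two-sided 0.05 and no dropout, all but the first assumed, the false-positive risk is about 8-10% if either outcome suffices, about 5% or less under Holm, and not inflated if both are required. The documents do not show which applies, so the finding is ambiguity and not demonstrated inflation. The stratification points are secondary: they affect power and whether every eligible child can be allocated. The change is worth making because it is cheap and fixes what the trial can conclude; pilot status limits its weight.

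**What to change.** Add to section 5.4 before outcome data are seen:

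1. One contrast per outcome, either the overall group-by-time test or one named visit, with other visits supportive. Name the itch instrument, its reporter (child or parent) and a small-sample method such as Kenward-Roger.
2. The rule, as one of: Holm across the two outcomes if either suffices; both at 0.05; or estimation only, with confidence intervals and no claim of efficacy.
3. The factors actually used in randomisation as covariates. Under Randomization Procedures these are gender for both outcomes and the itch-NRS stratum for CDLQI; modelled baseline itch can stand in for that stratum in the itch model. This corrects no error inflation but can gain power.
4. In sections 5.1 and 5.3, one consistent account of age, and a stratum for children admitted on POEM with itch NRS below 4.

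**Cost.** A few sentences and no new data. At 1 SD, Holm's first step costs about 7-11 points for a visit contrast if only one outcome responds. Requiring both costs more, as tabulated above, especially at 0.8 SD. Estimation only costs no power but gives up the efficacy claim. Covariates cost under 1 point if gender predicts nothing. A third itch band makes 2 × 3 = 6 cells averaging 24/6 = 4 children. Adding age as a two-level factor to the present four cells would make 8 averaging 24/8 = 3, so age should enter the model only if it is used in allocation.

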2. CDLQI

Secondary outcomes: All other questionnaires listed above.

## 6.0 Data Management

All of the data will be collected at Lurie Children’s hospital and saved on a secure research server that is maintained by Northwestern University. Survey data will be maintained within Northwestern University’s secure REDCap system. Only members of the authorized study team will have access to these systems.

Protected health information (PHI) necessary for study management (subject name and email addresses) is separated from the study data and non-PHI clinical data. This

provides additional data security to prevent unauthorized access or release of PHI. Subjects will be given a unique subject ID and that will be the link between PHI data and non-PHI clinical data. PHI will be marked appropriately in REDCap so data will not be exported with identifiers. Any review of data outside of the IRB-approved research team will be done only using de-identified data and/or summary tables or figures once the appropriate data use agreements are in place.

## **Data Storage for project**

The team will create a central database for storage of data on the FSM research server within the Department of Medical Social Sciences. Data will be deidentified with a separate coded identifier list with subject IDs.

## **7.0 Risks and Benefits to Subjects**

### **7.1 Risks:**

Because the study procedures take the form of interviews, there are no safety risks to consider in this study. Participation in this study does not involve any physical or emotional risk to participants beyond that of everyday life.

**Interviews and Questionnaires:** Interview participants and/or those completing questionnaires can choose to not answer a question, skip a question, request a break, or to stop/leave the interview/focus group at any time. Breaks will also be offered to participants throughout the interview. There is a very small risk of loss of confidentiality. Every measure to safeguard the information will be taken by the research team, including keeping all identifying in a locked cabinet and/or password-protected and keeping all questionnaire data de-identified using a study ID number.

**Audio Recordings:** There is a risk of loss of confidentiality with the audio recordings. Audio recordings will be destroyed after the study team has reviewed all interview notes and confirmed they are complete. In the interim, audio recordings will be kept in a secure, locked area to ensure access is only granted to the authorized research personnel.

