## 5.0 Procedures Involved

### 5.1 Overall Study Design

The overall study design is to develop a brief CBT intervention tailored to itch rumination via qualitative methods, including creating an interview guide with closed- and open-ended questions for stakeholders concerning itch-related distress and rumination. From these interviews, the itch rumination CBT will be created to address common fears and anxiety around itch, ruminative thoughts concerning itch, and other correlates associated with lowered quality of life in AD. This intervention will then be tested in a pilot RCT to compare the brief CBT intervention to usual care. Although therapists will not be blinded to intervention group, the research assistant assessing and analyzing outcomes with patients and their caregiver will be blinded to which intervention they received. Figure 1 summarizes our interventional model of CBT Itch.

Target Population: A convenience sample of children (8-17 years) with moderate-severe AD (and one parent) will be recruited from our group’s multidisciplinary AD clinic.

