## **8.0 Ethical Considerations**

### **8.1 Human Subjects Protection**

A periodic review must be submitted to the IRB at least once a year. The IRB must be notified of completion of the study. After study completion or termination, a final report must be provided to close the study. The investigator must maintain an accurate and complete record of all submissions made to the IRB, including a list of all reports and documents submitted. Adverse events must be submitted promptly to the IRB per IRB guidelines. At least once per year, the IRB must review and give written approval in order to continue the study. This trial will be conducted in accordance with Good Clinical Practices and the Declaration of Helsinki.

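### Section 7.1 dismisses safety risk because procedures are interviews, which does not describe the Aim 2 therapy, and with no planned ascertainment, adverse-event counts would not be comparable between arms

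*Combined protocol and SAP*

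**What the plan says.** Section 7.1 gives one reason for its safety conclusion: "Because the study procedures take the form of interviews, there are no safety risks to consider in this study". It continues: "Participation in this study does not involve any physical or emotional risk to participants beyond that of everyday life". The risks it then itemises concern interviews, questionnaires and audio recordings. Therapy is not among them.

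Section 5.1 says of the Itch CBT: "This intervention will then be tested in a pilot RCT to compare the brief CBT intervention to usual care". Section 5.3 (CBT arm) starts with a therapist assessment that covers mood and anxiety, among other topics, and goes on: "Therapists will then follow up with participants for three sessions on a weekly basis via telehealth on Northwestern Zoom". Participants are children aged 8-17 (Section 4.1).

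Section 8.1 states: "Adverse events must be submitted promptly to the IRB per IRB guidelines". The supplied text does not say what counts as an adverse event, who asks about it, when, or how it is recorded.

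The children's assessment table includes "PROMIS Pediatric Profile – Anxiety & Depression" at Visit 1, Visit 4 and Follow-Up, and a mood rating at all five time points. The parents' table adds proxy anxiety and depression. For the control arm, Section 5.3 says: "Participants in the Usual Care arm will complete the same schedule of study surveys". Section 5.4 makes all of these secondary outcomes.

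**The concern.** The stated ground for setting safety aside does not cover the part of the study in which a treatment is tested. Section 7.2 names the CBT intervention as a possible source of direct benefit, while Section 7.1 does not mention it as a possible source of risk.

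What is at stake is the interpretation of any adverse-event data. If events are not asked about, they are recorded only when someone happens to hear of them, and the arms differ in how much contact they have with study therapists. Section 2.0 says the pilot is meant to support an NIH application and, ideally, delivery in clinic or online. A harms record that cannot be interpreted would carry forward into that work.

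**Working it through.** The plan states no safety figure, so there is nothing to reproduce. The check sets the sections side by side.

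1. **Does the premise in 7.1 cover Aim 2?** Aim 1 (5.2) consists of semi-structured interviews with 20 dyads, and the premise fits. Aim 2 (5.1, 5.3) is a randomised comparison in which the CBT arm receives an assessment and three weekly therapist sessions with homework. The premise does not fit.

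2. **Is there a route from the 8.1 duty to a recorded event?** The children's table lists 12 instruments and the parents' table 9. None of the 21 asks about adverse events. Section 5.4 names two primary outcomes and assigns every other questionnaire to secondary status. It has no harms outcome and no by-arm summary of events.

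3. **Is opportunity to hear of an event equal across arms?**

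| Route | CBT | Usual care |
|---|---|---|
| Scheduled surveys (5.3) | 5 time points | 5 time points |
| Blinded research assistant assessing outcomes (5.1) | yes | yes |
| Care at the hospital (4.1) | yes | yes |
| Therapist sessions (1.0, 5.3) | 1 + 3 = 4, at 60 minutes each: 240 minutes | none |

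Three routes are shared. The fourth exists only in the CBT arm.

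4. **What does that do to counts?** Suppose each arm has *n* children and the same true event rate *p*, and an event is recorded with probability *d*. Expected recorded counts are *n·p·d*(CBT) and *n·p·d*(UC). Their ratio is *d*(CBT)/*d*(UC), which exceeds 1 whenever therapist contact adds any detection, even if the therapy has no effect on harms. The documents give no value for either *d*, so the direction can be argued but the size cannot be computed.

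5. **Do the symptom scores fill the gap?** In part. Mood, anxiety and depression are measured on the same schedule in both arms, so that comparison does not depend on therapist contact. But no safety use is stated, and a comparison of secondary outcomes is not a count of children who worsened. Events of other kinds are not covered.

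**The case against.** The strongest reply is that the plan is not silent. Section 8.1 makes reporting mandatory for the whole study. The symptoms most relevant to a psychological treatment are measured identically in both arms. Section 7.1 compares risk with everyday life, which is weaker than claiming zero risk. Section 5.3 also cites a screening questionnaire, an assessment interview and therapy materials that are not in the supplied text, and the consent pages were removed. Safety content there cannot be excluded.

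Much of this stands, and it rules out four stronger readings that a reader might infer:

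- **That nothing is collected.** Section 8.1 requires reporting, and the symptom scores exist in both arms. What is missing is systematic ascertainment and a by-arm summary.
- **That there is no comparison at all and usual-care events would go unseen.** Mood, anxiety and depression are compared as secondary outcomes, and usual-care families still have surveys, the research assistant and their clinicians. The imbalance concerns unsolicited events, which are less likely to surface there but not certain to be missed.
- **That 5.3, 7.1 and 8.1 all contradict one another.** Delivering therapy and reporting adverse events are compatible. The mismatch is between the rationale in 7.1 and the Aim 2 treatment. Section 8.1 is in tension with 7.1 and lacks a mechanism.
- **That the small sample sizes the defect.** With 12 per arm (24 dyads at 1:1), zero events gives a one-sided 95% upper limit of 1 − 0.05^(1/12) = 22.1%. The arithmetic is correct, but it holds for any arm of 12 and is unchanged by better ascertainment. The plan does not propose to infer absence of risk from the trial data.

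What does not stand is the suggestion that the 8.1 duty is enough. A duty to submit events, with no uniform way of finding them, leaves detection to depend on contact.

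**Conclusion.** The point holds in a limited form. The reason given in 7.1 is wrong for Aim 2, and the supplied text plans no systematic ascertainment or by-arm summary of adverse events. Unsolicited events are more likely to surface in the CBT arm, so counts by arm would not be comparable.

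The effect on counts has a direction but no computable size. The primary and secondary efficacy analyses are not affected. The conclusion rests on two assumptions: that the cited but unsupplied materials contain no uniform adverse-event enquiry, and that therapist sessions add some chance of hearing of an event beyond the routes both arms share. The change is worth making before recruitment because it is cheap and the information cannot be recovered afterwards on equal terms.

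**What to change.** 1. Reconcile 7.1 with 5.3 and 8.1: confine the interview rationale to Aim 1 and describe Aim 2 as a treatment trial.
2. Add one adverse-event item, worded identically, to the REDCap surveys already scheduled in both arms, with a short definition of what is to be recorded.
3. In 5.4, report counts by arm with exact intervals. Keep survey-solicited events separate from those reported to therapists, since only the former are gathered alike in both arms.
4. Tabulate by arm the number of children whose existing mood or depression scores worsen from Visit 1, with the definition of worsening fixed before the data are examined.

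The cost is a wording edit, one survey item per time point and a short descriptive table. Two limits remain. Families know their arm (Randomization Procedures), so self-report is unblinded, and therapists may still hear of more events in the CBT arm, which is why the two sources should not be pooled. How any response is handled clinically is for the investigators and the IRB.
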